5.4.3 DATA ANALYSIS PLAN

ANALYSIS OF GENOTYPES

We will analyze genotype-risk associations in the context of race or other known risk factors of PCa, and will investigate relationships between genotypes and tissue markers, disease progression and poor outcome. If we investigate the association using a priori hypotheses, we will use an unadjusted alpha = 0.05 as the cutoff for significance. If we do not use a priori hypotheses, we will adjust alpha appropriately. An a priori hypothesis would be based on existing knowledge that associates the genotype with cancer risk.

Data analysis will examine PCa occurrence, tumor stage, and outcome, in relation to allele variant genes and known risk factors of PCa. PCa cases will be grouped together and then examined separately by race. Allele variant genes will be categorized (homozygous wild-type, wild-type/mutant, homozygous mutant) for analysis. Other risk factors will also be examined as categorized variables, separated into subgroups of exposure (e.g., dichotomous, tertiles, quartiles). For an analysis by disease stage, we will stratify cases into two subgroups either by pathological stage ($\leq pT2$ versus $\geq pT3$) or by Gleason score (≤ 6 versus ≥ 7). The outcome variables that are studied will be relapse and/or survival. The relationship between PCa and risk factors will be examined by the chi-square test, and by odds ratios with 95% confidence intervals, using the homozygous

NCI IRB Approval:	
Protocol Number:	

October 28, 2004 05-C-N021

wild-type genotype (major allele), or the lowest exposure subgroup, as the reference group. Odds ratios and 95% confidence intervals will be calculated by unconditional logistic regression. Regression analysis will be performed in univariate and multivariate models to assess associations between risk factors and cancer susceptibility, and to adjust for possible confounding factors. Case-case analyses, correlating tissue marker expression with tumor staging, hormone blood concentrations, diet or genotypes, will be done by ANOVA, with the student's t-test, or a nonparametric test, such as the Mann-Whitney U rank sum test. To look at trends, the Mantel-Haenszel test for trend will be used to assess the correlation between marker expression/frequency and categorized (e.g., low, medium, high) variables, such as tumor stage, intake of a dietary factor, or IGF-1 blood concentrations. The association between a genotype and outcome will be studied either in a logistic regression model after categorizing into a good and poor outcome group or with the Kaplan-Meier method and the log-rank test. All analyses will be performed with the STATA and SAS statistical software packages.

ANALYSIS OF GENE EXPRESSION PROFILES

The data from the Affymetrix HG-U133A array will be estimated using the RMA procedure from Bioconductor (www.bioconductor.org). Previous analysis on raw data from replicate samples with RMA indicates that the mean standard deviation of log2 intensities is 0.1 across all intensity levels. This corresponds to a typical technical error of 5%-10% (94).

The factorial study design suggests an analysis of variance. We will first examine the four groups for heterogeneity of variances by comparing the ratios of variances between groups to the F-distribution. If the distributions conform, we will follow standard ANOVA procedure. If there is significant departure from agreement, we will perform non-parametric ANOVA using the rank F-test and use the Welch t-test for two group comparisons. We will select differentially expressed genes for contrasts between racial groups at each level of tumor, and for the difference between tumor stages across racial groups. To address the multiple comparisons problem we will use a modified FDR procedure of Benjamini and Hochberg adapted to correlated data (95).

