The power calculation assumes a study size of 400 cases and 400 controls which was the study size in the originally approved protocol. The study size was subsequently increased to 600/600 after approval of an amendment in 2006 to 1000/1000 after approval of an amendment in 2010. Power calculations were performed with the Power and Sample Size (PS) software, Version 2.1.30. William D. Dupont and Walton D. Plummer at the Vanderbilt University Medical Center have developed this software to conduct power calculations for clinical and epidemiological studies. The program is available on the Internet at http://www.mc.vanderbilt.edu/prevmed/ps/.

ANALYSIS OF ALLELE VARIANT GENES WITH ALL CASES GROUPED TOGETHER

We assume 1) a study population of 400 cases and 400 controls, and 2) two-sided alpha = 0.05, and 3) a prevalence of 5%, 20% or 40% for the disease-associated allele. We selected the candidate allele variants using the following criteria (and/or): 1) the allele variant gene is functionally important (literature), and 2) the polymorphism will likely affect protein expression/stability/activity or mRNA splicing/stability, and 3) the frequency of the rare allele is greater 5% in the general population. The power to detect an association between an allele variant and cancer risk at a given odds ratio is shown in Table 9.

Table	9
I GOIC	

Odds	5% Prevalence	20% Prevalence	40% Prevalence
ratio	Power	Power	Power
1.5	0.55	0.93	0.98
1.8	0.86	0.999	1
2	0.95	1	1
2.5	0.997	1	1

NCI IRB Approval:	October 28, 2004
Protocol Number:	05-C-N021

ANALYSIS OF ALLELE VARIANT GENES AFTER STRATIFICATION BY RACE

We assume 1) a study population of 200 cases and 200 controls, and 2) two-sided alpha = 0.05, and 3) a prevalence of 5%, 20% or 40% for the disease-associated allele. The power to detect an association between an allele variant and cancer risk at a given odds ratio is shown in Table 10.

Table 10

Odds	5% Prevalence	20% Prevalence	40% Prevalence
ratio	Power	Power	Power
1.5	0.35	0.71	0.82
1.8	0.62	0.95	0.99
2	0.76	0.99	0.998
2.5	0.94	1	1

DETECTION OF A GENE-ENVIRONMENT INTERACTION - ANALYSIS OF ALLELE VARIANT GENES AFTER STRATIFICATION BY EXPOSURE

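### For variants near the 5% allele-frequency limit, the three-genotype analysis has almost no homozygous-mutant men to compare and gives up about 7 to 11 power points against a one-degree-of-freedom test

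*Protocol*

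**What the plan says.** Section 5.4.3 (analysis of genotypes) fixes the coding: "Allele variant genes will be categorized (homozygous wild-type, wild-type/mutant, homozygous mutant) for analysis". It names the test and effect measure: "The relationship between PCa and risk factors will be examined by the chi-square test, and by odds ratios with 95% confidence intervals". The reference for genotypes is the homozygous "wild-type genotype (major allele), or the lowest exposure subgroup, as the reference group". Cases are analysed together and then by race, and logistic regression supplies the odds ratios. A trend test does appear, but it is attached to marker data: "the Mantel-Haenszel test for trend will be used to assess the correlation between marker expression/frequency and categorized" variables such as stage, diet or IGF-1. It is not named for genotype against case status.

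Section 5.4.2 lists as one criterion for candidate variants that "the frequency of the rare allele is greater 5% in the general population". The criteria are joined by and/or, so 5% is not even a strict floor. The power tables assume "a prevalence of 5%, 20% or 40% for the disease-associated allele", with one odds ratio per row and no genetic model. Table 9 rests on this: "We assume 1) a study population of 400 cases and 400 controls, and 2) two-sided alpha = 0.05". The current target in Table 7 is 1000 cases and 1000 controls, 500 and 500 per race. The study aims at odds ratios of 1.5 and above. Table 3 lists four example variants, at allele frequencies of 5-10%, 30%, 40% and 50%.

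**The concern.** The coding, the admission rule and the power basis do not fit together at low frequency. A variant carried at 5% leaves almost nobody in the homozygous-mutant column. Its odds ratio against homozygous wild type is then often undefined and otherwise too imprecise to use. A chi-square on the three-column table spends a second degree of freedom on that nearly empty column. The power tables describe something else: one factor at two levels, which is a comparison on one degree of freedom.

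Race-specific genetic risk is the study's stated emphasis, and the strata are smallest there. A low-frequency variant with an effect at the design target could be missed by race when the same data, coded as carriers, would have shown it.

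**Working it through.** **The plan's own power figure.** Table 9 gives 0.55, 0.93 and 0.98 at odds ratio 1.5 for prevalence 5%, 20% and 40%. With p1 = OR·p0 / (1 + (OR − 1)·p0), p̄ the mean of p0 and p1, and

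power = Φ{ [ |p1 − p0|·√n − 1.96·√(2p̄(1 − p̄)) ] / √(p0(1 − p0) + p1(1 − p1)) },

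p0 = 0.20 gives p1 = 0.30/1.10 = 0.2727. At n = 400 the power is Φ[(1.4545 − 1.1776)/0.5986] = Φ(0.463) = 0.678. The three prevalences give 0.275, 0.678 and 0.813 with 400 men per group, and 0.487, 0.929 and 0.981 with 800 alleles per group. The 20% and 40% entries therefore reproduce only if each man is counted twice. The 5% entry reproduces on neither basis with this formula. Either way it is a two-level calculation. The comparisons below do not use the printed powers.

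**Expected homozygous-mutant men at allele frequency q = 5%** (Hardy-Weinberg controls, an assumption): q² = 0.0025.
- Controls: 0.0025 × 500 = 1.25 per race; 0.0025 × 1000 = 2.5 pooled.
- Cases at per-allele odds ratio 1.5: 0.0025 × 2.25 / (0.9025 + 0.095 × 1.5 + 0.0025 × 2.25) = 0.005625/1.050625 = 0.00535, so 2.68 per race and 5.35 pooled.

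**Chance that the homozygous-mutant odds ratio has a zero cell.**
- By race: no such control, 0.9975^500 = 0.286; no such case, 0.99465^500 = 0.068; either, 1 − 0.714 × 0.932 = 0.335, in line with the simulated 34%.
- Pooled: 0.082 and 0.005; either, 0.086, about 9%.
- By race with no effect: 1 − 0.714² = 0.49.

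**Power of the tests** (simulation: multinomial genotypes, two-sided alpha 0.05, per-allele odds ratio 1.5, current sample size):

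| Setting | Three-category chi-square | Carrier | Trend | Homozygous-mutant contrast |
|---|---|---|---|---|
| By race, q = 5% | 0.47 | 0.56 | 0.58 | below 0.01 |
| Pooled, q = 5% | 0.78 | 0.85 | 0.87 | 0.06 |
| By race, q = 10% | 0.75 | 0.81 | 0.84 | 0.28 |
| Pooled, q = 10% | 0.968 | – | 0.985 | – |
| By race, q = 20% | 0.937 | – | 0.968 | – |

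The loss at 5% is 9 to 11 points by race and 7 to 9 pooled. By race at 10% it is 6 to 9 points, and about 10 under a dominant effect. Under a per-allele effect it falls to about 2 points pooled at 10% and 3 by race at 20%.

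With a dominant odds ratio of 1.5 at q = 5%, the figures are 0.44 against 0.54 for carriers by race, and 0.74 against 0.82 to 0.83 pooled. With no effect, the three-category test at 5% rejects in only about 3.4 to 4.0% of studies, so it is conservative.

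**The case against.** **Reach.** A reader might infer that the homozygous-mutant contrast is empty, and the power loss 7 to 11 points, for variants in general. The documents do not support that. Three of the four Table 3 variants lie at 30-50%. At q = 20% and 40% one expects 40 and 160 homozygous-mutant controls in 1000, and the contrast is estimable. Even at 5%, the pooled contrast is very imprecise but usually not empty. The one low-frequency example in Table 3 has a reported odds ratio of 2.4. Taken as a per-allele effect at 5% by race, that gives the three-category test 0.997 against 0.999 for trend, so the overall test loses nothing there. The homozygous-mutant odds ratio still rests on 1.25 expected controls.

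**Replacing the test everywhere.** A per-allele test for all variants may look like the obvious cure, but it is a trade-off. By race, a recessive odds ratio of 1.8 at q = 20% gives the three-category test 0.44 against about 0.27 for trend. A dominant odds ratio of 1.5 at q = 50% gives 0.65 against 0.55. In the other direction, a carrier test gains 7 to 8 points by race if the effect is dominant at 20% or 40%. For common variants in an exploratory study with no stated genetic model, three categories are a defensible choice.

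**Flexibility of the text.** The protocol does not call the three-category chi-square the sole significance test. It does not forbid collapsing, and an analysis plan not shown here could add a sparse-cell rule. That is fair, and the absence of such a rule is not the point. The point is that the protocol states a coding, a test and a reference group that do not suit variants it admits, and sizes the study on a different comparison.

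**Printed powers.** One might also read this as showing that the power tables are wrong. Their basis in men or alleles is a separate question, and nothing here depends on it.

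**Conclusion.** The point holds for low-frequency variants. Near 5% allele frequency, the stated coding yields a homozygous-mutant odds ratio that is unusable by race and close to it pooled. At an odds ratio of 1.5, the three-category chi-square loses about 7 to 11 points against a carrier or trend test. By race the loss persists at 10%. Above that, the sparse-cell problem disappears and the choice of test depends on the unknown genetic model. Separately, the power in 5.4.2 is for a two-level factor and does not describe the three-category analysis at any frequency.

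The figures assume Hardy-Weinberg proportions in controls, the 2010 target sizes and the genetic models named; the protocol gives no genetic model. If its prevalence means carriers and not alleles, 5% corresponds to an allele frequency of about 2.5%, and only 0.32 homozygous-mutant controls are expected in 500.

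**What to change.** In 5.4.3, add a rule. Where the expected homozygous-mutant count among cases or controls in the analysed stratum is below about 5, combine homozygous-mutant with heterozygous men. Use the one-degree-of-freedom carrier test, with the carrier odds ratio against homozygous wild type, as the significance test. The expected count should come from the genotype totals of cases and controls together, so that the choice does not depend on the comparison itself. With q = √(5/n), the rule acts below an allele frequency of about 10% by race (n = 500) and about 7% pooled (n = 1000). Between those values the two analyses of one variant would be coded differently, and the report should say so.

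Keep the three-category analysis for commoner variants. A per-allele trend test may be added there, but not as a replacement.

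In 5.4.2, name the test and genetic model behind the power, and restate the power for the test actually used.

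The cost is wording and a recoded variable, with no new data. The downside is that a recessive effect of a rare variant is no longer tested separately. Little is lost: at 5% frequency and a recessive odds ratio of 2.4, the three-category test has power of only about 0.07 by race (carrier 0.05) and 0.16 pooled.

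### Section 5.4.3 names only categorised forms for continuously measured exposures, with no continuous term and no trend test for prostate cancer risk; the cost is avoidable power, and the point is minor

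*Protocol*

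**What the plan says.** Protocol section 5.4.3 (Analysis of Genotypes) fixes the form of the non-genetic exposures: "Other risk factors will also be examined as categorized variables, separated into subgroups of exposure (e.g., dichotomous, tertiles, quartiles"). The case-control methods follow: "The relationship between PCa and risk factors will be examined by the chi-square test, and by odds ratios with 95% confidence intervals", with the homozygous major-allele genotype or the least-exposed category as reference. The model is named next: "Odds ratios and 95% confidence intervals will be calculated by unconditional logistic regression". Adjustment is covered by "Regression analysis will be performed in univariate and multivariate models to assess associations between risk factors and cancer susceptibility"; a second purpose given for these models is "to adjust for possible confounding factors". The covariates and their coding are not listed.

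The only trend test in the section concerns tumour markers: "To look at trends, the Mantel-Haenszel test for trend will be used to assess the correlation between marker expression/frequency and categorized" variables, which are described as "categorized (e.g., low, medium, high) variables, such as tumor stage, intake of a dietary factor, or IGF-1 blood concentrations". Case-case analyses otherwise use ANOVA, the t-test or a rank test.

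Two other places bear on the point. The gene-environment power calculations in 5.4.2 put exposure into quartiles and assume a linear trend in a logistic model. The secondary objectives in 1.1 plan to correlate serum IGF-1 with tissue markers.

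**The concern.** IGF-1, hormones, dietary intake and amount smoked are measured on, or close to, a continuous scale. Section 5.4.3 groups them before the risk analysis. Because the odds ratios are taken against the least-exposed category, the logistic models rest on the same groups. An unordered chi-square on k groups also spends k − 1 degrees of freedom and ignores their order. The linear trend that 5.4.2 relies on for exposure therefore has no matching case-control test in 5.4.3.

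Environmental exposure and its interaction with genotype are part of the primary hypothesis in the protocol's opening summary, and race-specific analyses are planned on half the sample. Power given up through coding matters most there. If confounders were grouped in the same way, part of their confounding would also survive adjustment.

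**Working it through.** The protocol gives no figure for the loss from grouping, so there is none to reproduce.

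**Inputs.** From the protocol: 1000 cases and 1000 controls, 500/500 per race (Table 7); two-sided alpha 0.05 and a design odds ratio of 1.5 (5.4.2). Applying that 1.5 to the top versus the bottom quartile of an exposure is my choice. Assumed: a normal exposure, a log-linear effect, a small effect size and equal-sized groups.

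**Information kept.** With k equal groups cut at normal quantiles q, the group means are m_j = k[φ(q_{j−1}) − φ(q_j)], and the share kept is R = mean(m_j²).

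- Median split: means ±0.798, R = 0.637, loss 36%.
- Tertiles: means −1.091, 0, 1.091, R = 0.793, loss 21%.
- Quartiles: means ±1.271 and ±0.325, R = 0.861, loss 14%. With integer trend scores s, the share is mean(s·m)²/mean(s²) = 1.0345²/1.25 = 0.856.

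**Effect size.** The outer quartile means differ by 2.542 SD. An odds ratio of 1.5 across that gap gives b = ln(1.5)/2.542 = 0.1595 per SD, or an odds ratio of 1.17 per SD.

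**Noncentrality.** λ = b² × N × 0.25. For N = 2000, λ = 0.02544 × 500 = 12.72. For N = 1000, λ = 6.36. Each grouped test uses λ times the share kept. At N = 2000 the chi-square values are 8.10 (1 df), 10.09 (2 df) and 10.95 (3 df).

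| Analysis | df | Power 1000/1000 | Power 500/500 |
|---|---|---|---|
| Continuous term | 1 | 0.95 | 0.71 |
| Quartile trend | 1 | 0.91 | 0.65 |
| Median split chi-square | 1 | 0.81 | 0.52 |
| Tertile chi-square | 2 | 0.82 | 0.51 |
| Quartile chi-square | 3 | 0.80 | 0.48 |

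Finer groups do not help the unordered test, because the information gained is spent on degrees of freedom. Measured by the sample needed for 80% or 90% power, its loss is about 34 to 38% at two, three or four groups.

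**Sensitivity to the distribution.** With the effect linear on the raw scale, the 1-df loss from quartiles to a median split is 6 to 25% for a uniform exposure, 26 to 52% for an exponential one and 25 to 48% for a lognormal one with log-SD 0.5.

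**Residual confounding, if confounders were grouped.** For a normal confounder in a linear model with exposure-confounder correlation ρ, the share of bias left is (1 − R)/(1 − ρ²R). For ρ from 0.1 to 0.5 this is 37 to 43% (two groups), 21 to 26% (three) and 14 to 18% (four).

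**The case against.** A reader might infer from 5.4.3 that exposures are analysed by chi-square alone. They are not: the same passage gives logistic odds ratios, univariate and multivariate models, ANOVA, t-tests or rank tests for case-case work, and a trend test for markers. Nor is the number of groups capped at four, since the list of groupings is given as examples. The 14 to 36% loss should not be attached to the chi-square test either; it belongs to a 1-df use of the groups. All of this stands.

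The odds ratio of the top against the bottom quartile is itself a 1-df contrast. At 1000/1000 each quartile holds about 500 men, so the variance of the log odds ratio is about 2/(500 × 0.25) = 0.016. With ln(1.5)² = 0.1644, the noncentrality is 10.28 and power is about 0.89. At 500/500 the noncentrality is 5.14 and power about 0.62. A reader who relies on that one contrast loses less than the chi-square rows suggest, though 5.4.3 does not single it out as the test.

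Every grouped analysis also reaches about 80% power in the full sample at the 1.5 threshold. Quantile groups do not impose a log-linear shape, and 5.4.2 calls the study exploratory. These arguments limit the severity. They do not give a reason to leave out a continuous term or a trend test when the values are collected and logistic models are fitted anyway.

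**Conclusion.** The point holds as a minor inefficiency in a stated method. The protocol prescribes grouped exposures, leaves the groupings open, and provides neither a continuous term nor a case-control trend test to match the linear trend assumed in 5.4.2. In the full sample, power at the design threshold falls from 0.95 to between 0.80 and 0.82 by chi-square. Within one race it falls from 0.71 to between 0.48 and 0.52. These figures rest on a normal exposure and a log-linear effect, and the loss changes with the distribution.

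Two stronger readings are not supported. One is that the study will leave residual confounding. The protocol does not say how adjustment covariates are coded, and that may be settled in an analysis plan not seen here, so the 14 to 43% is conditional. The other is that the main genetic objective is weakened. Genotype has three natural levels and is untouched.

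**What to change.** In 5.4.3:

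- Make the primary test of each continuously measured exposure a 1-df term in the logistic model, per SD and on the log scale if skewed, with a spline check of linearity.
- Enter continuous confounders as continuous or spline terms.
- Carry out the IGF-1 and tissue-marker correlation planned in 1.1 as a rank correlation on the measured values.
- Keep quartile odds ratios for display, with cut points taken from the controls.

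The cost is a few sentences and one linearity check per exposure. Data and software stay the same.

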1.2.2 RATIONALE FOR SELECTION OF SUBJECTS BY RACE

PCa has the largest health disparity for any cancer site in the US (52). The causes of this health disparity are multifactorial and may include tumor biology. African-American men have the highest incidence and mortality rates. The disease accounts for about 39% of all cancers diagnosed in African-American males (53). The age-adjusted African-American to Caucasian cancer incidence ratio is about 1.6 but the mortality rate is 2 to 3-fold higher for African-Americans than Caucasians (22). African-American men develop PCa at a younger age, and the disease progression is faster than in Caucasians (22). It is hypothesized that the tumor biology of PCa is different in the two ethnic groups.

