2.1.1 INCLUSION CRITERIA

CASES

- 1. Has been diagnosed with PCa within the last two years
- 2. Pathological diagnosis of PCa made
- 3. Must reside in Baltimore City or contiguous metropolitan counties, Anne Arundel and Prince George's counties, Eastern Shore, western and northern Maryland, or adjacent counties in Pennsylvania, Delaware, Virginia, or Washington DC area
- 4. Has a residential working phone within his home
- 5. Was born in the United States
- 6. Of African-American or Caucasian descent, and age 40 to 90 years
- 7. Speaks English well enough to be interviewed
- 8. Is physically and mentally capable of performing the interview
- 9. Never has been interviewed as a control for the study
- 10. A non-objection statement to contact the patient has been obtained from the treating physician at the hospital where the patient was identified, or from the physician who is listed as the treating physician

CONTROLS

- 1. Stratified to match cases by age (5-year intervals), gender and race
- 2. Must reside in Baltimore City or contiguous metropolitan counties, Anne Arundel and Prince George's counties, Eastern Shore, western and northern Maryland, or adjacent counties in Pennsylvania, Delaware, Virginia, or Washington DC area
- 3. Has a residential working phone within his house
- 4. Was born in the United States
- 5. Speaks English well enough to be interviewed
- 6. Is physically and mentally capable of performing the interview
- 7. Never has been interviewed as a control for the study (with our tracking database)

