5.4 STATISTICAL SECTION

5.4.1 SUMMARY OF STUDY DESIGN AND OBJECTIVES

As of 2010, our last amendment for the study, we are proposing an epidemiological prostate cancer case-control study that will include 1000 prostate cancer cases and a sample of 1000 population-based controls (Table 7). The aim of the study is to identify genetic susceptibility factors for nonhereditary PCa with a particular emphasis on genetic factors that might explain the comparatively aggressive nature of PCa in African-American men. The accrual time is projected to end in 2014/2015, averaging an annual accrual of 120 cases and 120 frequency-matched controls. The participants will be African-American and Caucasian males.

Women are excluded from the study because they do not develop PCa. Men, who are younger than 40 years and older than 90 years are excluded. Nonhereditary PCa is rare at an age younger than 40 years. PCa patients, who are older than 90 years, are excluded because of co-morbidity considerations. Subjects with a race/ethnic background other than African-American or Caucasian have been excluded. Less than 10% of the PCa patients at the 2 participating hospitals have a racial/ethnic background that is not African-American or Caucasian. The inclusion of such a small number of cases would not allow a risk analysis based on stratification by race.

The primary objectives of the study are to examine the association of 1. allele variant genes with PCa risk and outcome, and 2. exposures with gene expression profiles in prostate tumors. The objective will be accomplished with 1) genotype analysis of blood DNA from 1000 cases and 1000 controls, 2) collection of data from questionnaires, medical and pathology records, and the National Death Index, and 3) expression profiling of fresh-frozen tumor samples.

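### The genotype-outcome analysis permits a good/poor split with no time horizon, and its pooled test names no control for race

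*Protocol*

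**What the plan says.** Section 5.4.1 of the Protocol makes the association of variants with risk and outcome a primary objective. Section 5.4.3 then fixes how outcome is analysed:

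- Endpoints: "The outcome variables that are studied will be relapse and/or survival".
- Method: "either in a logistic regression model after categorizing into a good and poor outcome group or with the Kaplan-Meier method and the log-rank test". The sentence gives no horizon for good or poor, no time origin, no covariates and no strata.
- Scope: "Data analysis will examine PCa occurrence, tumor stage, and outcome, in relation to allele variant genes and known risk factors of PCa".
- Race, in the next sentence: "PCa cases will be grouped together and then examined separately by race".
- Covariate adjustment: regression models are planned "to assess associations between risk factors and cancer susceptibility, and to adjust for possible confounding factors". This wording is about susceptibility, and outcome is not mentioned.
- Significance: 0.05 without adjustment where there is an a priori hypothesis.

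Three other places matter:

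- **Accrual.** The 12-month pilot was completed in 2006 and its participants count toward the total (section 3). For the end of accrual, section 5.4.1 says "The accrual time is projected to end in 2014/2015".
- **Entry.** A case qualifies if he "Has been diagnosed with PCa within the last two years" (section 2.1.1).
- **Race and outcome.** Section 1.2.2 says the "incidence ratio is about 1.6 but the mortality rate is 2 to 3-fold higher for African-Americans than Caucasians", and the Introduction describes more rapid progression in African-American men. Section 1.2.3 reports a racial gradient in the frequency of one SRD5A2 variant, without figures.

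**The concern.** There are two separate weaknesses and one smaller gap.

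**The good/poor split.** With accrual spread over nine to ten years, potential follow-up differs widely between men. Without a horizon, a man enrolled late who has not yet relapsed can be classed with men who have stayed free of relapse for many years. The logistic option therefore mixes outcome with length of observation.

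**The pooled test.** This is a comparison among cases only, so frequency matching of controls to cases gives no protection. The Protocol links race to outcome and, for at least one variant, to allele frequency. If both links hold for a given variant, a pooled test without a race term can attribute the race difference in outcome to the variant. Section 3.1.5 recognises that racial heterogeneity can create spurious genetic differences, but its remedies (matching and a restricted catchment area) serve the case-control contrast.

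**Late entry.** Men who die between diagnosis and enrolment are never observed. Survival timed from diagnosis without delayed entry is then too favourable. The plan names no time origin.

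**Working it through.** The Protocol gives no power, event count or error rate for the outcome analysis, so there is no stated figure to reproduce.

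**1. Misclassification under the good/poor split**

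Assumptions: exponential time to relapse, 25% relapse by five years, follow-up uniform over 0-10 years.

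- Rate: λ = −ln(0.75)/5 = 0.0575 per year.
- Mean relapse time among five-year relapsers: 1/λ − 5 × 0.75/0.25 = 17.38 − 15 = 2.38 years.
- A relapse at time T is missed with probability T/10, so the share missed is 2.38/10 = 0.238, about 24%.

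If every man has at least one year (uniform over 1-10), the share is E[(T − 1)⁺ | T < 5]/9 = 1.49/9, about 17%. It is zero if all men have five years.

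**2. Size of the race effect among cases**

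Mortality ratio 2 to 3 and incidence ratio 1.6 (section 1.2.2) give 2/1.6 = 1.25 to 3/1.6 = 1.88, about 1.9. This is a crude ratio of population rates, not a hazard ratio among cases.

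**3. Bias in the pooled hazard ratio for a null variant**

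With 500 cases per race (Table 7), carrier frequencies a (African-American) and c (Caucasian), and race hazard ratio r:

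- African-American share of carriers: s₁ = a/(a + c).
- African-American share of non-carriers: s₀ = (1 − a)/(2 − a − c).
- Pooled HR ≈ [1 + (r − 1)s₁]/[1 + (r − 1)s₀].

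For 60/20%: s₁ = 0.6/0.8 = 0.75 and s₀ = 0.4/1.2 = 0.333. At r = 1.9 the HR is 1.675/1.300 = 1.29; at r = 1.25 it is 1.188/1.083 = 1.10. For 40/30%: s₁ = 0.571 and s₀ = 0.462, giving 1.07 at r = 1.9 and 1.02 at r = 1.25.

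**4. Type I error by simulation**

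The variant has no effect. Cases are 500 + 500, with 600 replicates per row and a two-sided 0.05 test. Assumed: hazard 3% per year in Caucasian cases, entry uniform 0-2 years after diagnosis, follow-up uniform 1-10 years after entry, and the carrier frequencies shown.

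| Race HR | Carriers | Pooled log-rank | Pooled good/poor | Race-stratified log-rank |
|---|---|---|---|---|
| 1.25 | 40/30% | 0.065 | 0.060 | 0.060 |
| 1.25 | 50/20% | 0.077 | 0.073 | 0.048 |
| 1.25 | 60/20% | 0.107 | 0.095 | 0.060 |
| 1.9 | 40/30% | 0.075 | 0.077 | 0.055 |
| 1.9 | 50/20% | 0.313 | 0.292 | 0.048 |
| 1.9 | 60/20% | 0.462 | 0.438 | 0.048 |

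The simulation standard error near 0.05 is √(0.05 × 0.95/600) = 0.009.

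Rough check of the last row (205 events on average, 40% carriers): z = ln(1.288) × √(205 × 0.4 × 0.6) = 0.253 × 7.01 = 1.78, and Φ(1.78 − 1.96) = 0.43, close to the simulated 0.46.

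**5. Which feature causes the false positives**

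With equal carrier frequency (30/30%), the error of the pooled tests stays at 0.035-0.057 for race hazard ratios from 1.0 to 2.5, despite unequal follow-up and late entry. Using delayed-entry risk sets changes the pooled log-rank error by at most about 0.01. Only the race difference in carrier frequency, combined with a race difference in outcome, inflates the error.

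**The case against.** The strongest reply is that race is not ignored. The sentence on analysing cases by race follows directly after outcome is named, and within-race analysis removes the confounding. This stands. A reader who stopped at the pooling half of that sentence might infer that the plan overlooks race, and the text does not support that. What remains is that the pooled test comes first, can be declared significant at 0.05, and has no stated rank against the within-race results. Splitting also leaves 500 cases per analysis, whereas a stratified test uses all 1000.

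A reader might also infer that unequal follow-up and late entry make null variants look prognostic. The simulation does not show this when both are unrelated to genotype within race. Kaplan-Meier with log-rank censors properly, so unequal follow-up counts only against the logistic option. Two years is also a maximum for entry: section 2 describes daily case finding and expects to recruit most men weeks or months before surgery or other treatment.

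The sizes rest on assumptions. In a further simulation with baseline hazards of 1-5% per year and follow-up of 0.5-10 years, pooled log-rank error for carriers of 40/30% stayed at 0.05-0.09. For 50/10% at a race hazard ratio of 1.9 it ran from 0.23 to 0.64. The Protocol gives neither event rates nor carrier frequencies by race, and it does not say that men with short follow-up count as good.

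Finally, covariates and time origin may sit in an analysis plan not shown here, and section 5.4.2 calls the study exploratory, with findings to be validated. Both points temper the consequence. Neither cures the choice of method that the Protocol itself makes.

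**Conclusion.** The point holds in limited form. The good/poor logistic option is poorly specified for a nine-to-ten-year accrual: about 24% of five-year relapsers would be missed under the stated assumptions, fewer with a longer minimum follow-up. The pooled outcome test names no race term, and a null variant can look prognostic in it. Error is near nominal to about 0.11 at a race hazard ratio of 1.25, and about 0.08 to 0.46 at 1.9, for carriers of 40/30% to 60/20%. Stratifying by race brings it back to about 0.05.

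It would go too far to say that race confounds every pooled result, or that null variants will look prognostic. Both a race effect on outcome and a race difference in that variant's frequency are needed. Late entry bears on curves and estimates timed from diagnosis only. Because outcome is a primary objective and the remedy is cheap, the change should be made.

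**What to change.** In section 5.4.3:

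- Replace the horizon-free good/poor option with a time-to-event analysis. As the pooled test, use a race-stratified log-rank test or a Cox model stratified by race and adjusted for age.
- Report the within-race results alongside, and state which result governs.
- Count time from enrolment, or from diagnosis with delayed entry at enrolment, and censor at last follow-up.
- If a binary outcome is kept, define it at a fixed horizon among men with that much follow-up, and adjust for race.
- Do not adjust for stage and Gleason score by default. Both may lie on the path from genotype to outcome, and the plan studies stage as an endpoint. Use them in a secondary model only.

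The cost is slightly more analysis work. Follow-up dates must be abstracted from the sources in section 3.1.3, which lists where outcome information comes from but does not mention a date of last follow-up. Recruitment and sample size do not change.
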